## 10.6. Appendix 6: Country-Specific Requirements

### 10.6.1. Italy

#### 10.6.1.1. Exclusion Criteria

In addition to the discontinuation criteria in [Section 7.1.1.1](#) & [Section 7.1.1.2](#) the following additional exclusion criteria will apply to participants enrolled in Italy.

Moderate or severe renal impairment CrCL GFR <60 mL/min/1.73m^2 (Calculated GFR based on updated “bedside” Schwartz formula for pediatric patients (CrCL (mL/min/1.73 m^2) = 0.413 \* Height (cms)/ Serum cr (mg/dL) or hepatic impairment (AST/ALT >1.5 ULN).

#### 10.6.1.2. Discontinuation Criteria

In addition to the other discontinuation criteria in [Section 7](#), Participants who completed Tanner stage V should be considered to have completed puberty and be discontinued from the study.

#### 10.6.1.3. Data Monitoring Committee

This study will use an eDMC. The eDMC is independent of the study team and includes internal Pfizer members. The eDMC charter describes the role of the eDMC in more detail. The eDMC will be responsible for ongoing monitoring of the efficacy and safety of participants in the study according to the charter. The recommendations made by the eDMC will be forwarded to the appropriate authorized Pfizer personnel for review and final decision. Pfizer will communicate such decisions, which may include summaries of aggregate analyses of endpoint events and of safety data that are not endpoints, to regulatory authorities, investigators, as appropriate.

#### 10.6.1.4. Contraception Methods

Due to the age of the participants, length of the study, and in accordance with the Clinical Trials Facilitation and Coordination Group (CTFG) - Recommendations related to contraception and pregnancy testing in clinical trials Version 1.1. The following revisions have been made to the contraceptive requirements.

The addition of alternatives to sexual abstinence including highly effective hormonal contraceptives and barrier methods are to be used depending on participant preference and local guidelines as appropriate. The requirements of one highly effective method and duration of contraceptive use remain unchanged.

1. Combined (estrogen- and progestogen-containing) hormonal contraception associated with inhibition of ovulation:
  - Oral + barrier\*;
  - Intravaginal + barrier\*;

- Transdermal + barrier\*.
2. Progestogen-only hormone contraception associated with inhibition of ovulation:
- Oral + barrier\*;
  - Injectable + barrier\*.

\*Acceptable barrier methods to be used concomitantly with options above for the study include any of the following:

- Male or female condom, with or without spermicide;
- Cervical cap, diaphragm, or sponge with spermicide;
- A combination of male condom with either cervical cap, diaphragm, or sponge with spermicide (double-barrier methods).

### **10.6.2. Denmark**

The following requirements apply for Denmark, in accordance with local regulation; Section 11 The Danish Medicines Agency's guidance on the implementation of decentralised elements in clinical trials with medicinal products Version 2.0, September 2021.

#### **10.6.2.1. Preparation & Dispensing**

Recifercept may be shipped by an appropriate third-party courier or study investigator to study participants if permitted by local regulations and in accordance with storage and transportation requirements for recifercept. The overall responsibility for IMP activities remains with the study investigator as per ICH GCP Section 4.0.

#### **10.6.2.2. Participant Compliance and Home Administration**

A home health care service may be utilized to facilitate certain activities per the [SoA](#), in the event of a public emergency, such as COVID-19 or when additional caregivers are trained, see [Appendix 10.7.5 Home Health Visits](#).

All home health care nurses and their responsibilities are recorded on the delegation of authority log. However, the study investigator maintains overall responsibility for all trial activities as per ICH GCP Section 4.0.

In the event that any visits are conducted in the home, a report is provided to the site detailing the assessments conducted, including any completed source documents that were collected to be included in the eCRF and participants medical file.

Any requests for home health support should be submitted to the sponsor for approval.

CCI

## 10.7. Appendix 7: Alternative Measures During Public Emergencies

The alternative study measures described in this section are to be followed during public emergencies, including the COVID-19 pandemic. This appendix applies for the duration of the COVID-19 pandemic locally and will become effective for other public emergencies only upon written notification from Pfizer.

Use of these alternative study measures are expected to cease upon the return of business as usual circumstances (including the lifting of any quarantines and travel bans/advisories).

### 10.7.1. Telehealth Visits

In the event that in-clinic study visits cannot be conducted, every effort should be made to follow up on the safety of study participants at scheduled visits per the [SoA](#) or unscheduled visits. Telehealth visits may be used to continue to assess participant safety and collect data points. Telehealth includes the exchange of healthcare information and services via telecommunication technologies (eg, audio, video, video-conferencing software) remotely, allowing the participant and the investigator to communicate on aspects of clinical care, including medical advice, reminders, education, and safety monitoring. The following assessments must be performed during a telehealth visit:

- Review and record study intervention(s), including compliance and missed doses.
- Review and record any AEs and SAEs since the last contact. Refer to [Section 8.3](#).
- Review and record any new concomitant medications or changes in concomitant medications since the last contact.
- Review and record contraceptive method and results of pregnancy testing. Confirm that the participant is adhering to the contraception method(s) required in the protocol. Refer to [Appendix 4](#) and [Section 10.4.4](#) of this appendix regarding pregnancy tests.

Study participants must be reminded to promptly notify site staff about any change in their health status.

### 10.7.2. Alternative Facilities for Safety Assessments

#### 10.7.3. Laboratory Testing

If a study participant is unable to visit the site for protocol-specified safety laboratory evaluations, testing may be conducted at a local laboratory if permitted by local regulations. The local laboratory may be a standalone institution or within a hospital. The following safety laboratory evaluations may be performed at a local laboratory:

- See table of safety labs in [Appendix 2](#).

If a local laboratory is used, qualified study site personnel must order, receive, and review results. Site staff must collect the local laboratory reference ranges and certifications/ accreditations for filing at the site. Laboratory test results are to be provided to the site staff as soon as possible. The local laboratory reports should be filed in the participant's source documents/medical records. Relevant data from the local laboratory report should be recorded on the CRF.

If a participant requiring pregnancy testing cannot visit a local laboratory for pregnancy testing, a home urine pregnancy testing kit with a sensitivity of at least 25 mIU/mL may be used by the participant to perform the test at home, if compliant with local regulatory requirements. The pregnancy test outcome should be documented in the participant's source documents/medical records and relevant data recorded on the CRF. Confirm that the participant is adhering to the contraception method(s) required in the protocol.

#### **10.7.4. Study Intervention**

If the safety of a trial participant is at risk because they cannot complete required evaluations or adhere to critical mitigation steps, then discontinuing that participant from study intervention must be considered.

Recifercept may be shipped by an appropriate third-party courier to study participants if permitted by local regulations and in accordance with storage and transportation requirements for recifercept. Pfizer does not permit the shipment of recifercept by mail. The tracking record of shipments and the chain of custody of recifercept must be kept in the participant's source documents/medical records.

Study intervention can continue to be administered at home in accordance with the protocol.

#### **10.7.5. Home Health Visits**

A home health care service may be utilized to facilitate scheduled visits per the [SoA](#). Home health visits include a healthcare provider conducting an in-person study visit at the participant's location, rather than an in-person study visit at the site. The following may be performed during a home health visit:

- Support of home dosing in accordance with the protocol;
- Blood draws;
- Administer PROs.

#### **10.7.6. Adverse Events and Serious Adverse Events**

If a participant has COVID-19 during the study, this should be reported as an AE or serious SAE and appropriate medical intervention provided. Study treatment should continue unless the investigator/treating physician is concerned about the safety of the participant, in which case temporary or permanent discontinuation may be required.

It is recommended that the investigator discuss temporary or permanent discontinuation of study intervention with the study medical monitor.

#### **10.7.7. Efficacy Assessments**

Anthropometric measurements cannot be undertaken in the participant's home. Administration of PRO/ObsRO and blood draws may be undertaken by home health teams.

#### **10.7.8. Internal Review Committee**

An internal review committee will assess the safety and, where relevant, PK data on a regular basis.

The IRC will continue to meet via teleconference in accordance with the IRC charter.

## 10.8. Appendix 8: SC Dosing Instructions

### SC DOSING INSTRUCTIONS

#### GENERAL INSTRUCTIONS

- Allow prepared syringes with the medication to reach ambient temperature for 15 minutes prior to administration (they should not be cold to touch);
- Never reuse needles or syringes;
- Dispose of all used materials in the appropriate sharps container and return used vials into the cartons to be checked by a study monitor.

#### **Gather your supplies:**

- Alcohol pads;
- Prepared syringe with medication;
- Puncture resistant sharps container.

[figure not shown]
#### **Choose 1 of the recommended injection sites described below:**

The injection(s) should be given when participant is sitting or lying down into the **abdomen or outer thighs**. **The back of the arms may be used as an alternative injection site (Figure 1).**

**Do not inject into areas where the skin is tender, bruised, red, or hard. Avoid areas with scars, moles and avoid the area 1 inch from the naval.**

- Injections should start in either the abdomen or outer thighs at number 1 and proceed in a clockwise manner from site number 1 through to number 4.
- If injections are given in the back of the arms, alternate between the left and right arms.
- For each injection given (including if 2 injections are needed for 1 dose), a new injection site must be chosen. Inject at least 2 inches from the previous site.

[figure not shown]
**Figure 1. Injection Site Rotation**

**Preparing the subcutaneous injection site and injecting Recifercept**

[figure not shown]
3. Wash hands thoroughly with soap and water prior to any injections.
4. Choose the site from Figure 1 and clean the site where Recifercept is to be injected with a new alcohol swab, using a circular motion, starting from the inside and working to the outside of the chosen injection site. Allow the area to dry thoroughly, do not blow the area dry. DO NOT touch this area again before giving the injection.
5. Using the thumb and forefinger, lift up a fold of skin with one hand (Figure 2).

**Figure 2. Technique for Holding Skin Prior to Injection**

[figure not shown]
6. With the other hand, hold the syringe like a pencil with the bevel up. With a quick, short motion, push the needle into the skin at an angle of 45° (Figure 3).

**Figure 3. Injection Angle**

7. Once the needle has been pushed into the skin, release the pinched skin while still holding the needle in place. With your free hand, push the plunger all the way down at a slow, steady rate to deliver the entire contents of the syringe (Figure 4).

**Figure 4. Technique for Injecting Study Intervention**

8. When the syringe is empty, remove the needle from the skin; be careful to keep it at the same angle it was when it was inserted into the skin. Place the syringe/needle in the sharps container provided.
9. Repeat steps 1 through 5 if a second syringe is required for the total dose.
10. Slight bleeding may occur. Cover with a sterile gauze pad if needed. DO NOT rub the injection site. You may place a band aid over the injection site.

## 10.9. Appendix 9: Abbreviations

The following is a list of abbreviations that may be used in the protocol.

Abbreviation	Term
Abs	absolute
ADA	antidrug antibodies
ADA -	antidrug antibody negative
ADA +	antidrug antibody positive
ADL	activities of daily living
AE	adverse event
AIFA	Agenzia Italiana del Farmaco
AESI	adverse events of special interest
ALT	alanine aminotransferase
ANOVA	analysis of variance
AST	aspartate aminotransferase
β-hCG	beta-human chorionic gonadotropin
BIW	Twice-weekly
BMI	Body mass index
BUN	blood urea nitrogen
CFR	Code of Federal Regulations
CCI	
CIOMS	Council for International Organizations of Medical Sciences
CK	creatine kinase
CL/F	clearance
CCI	
COA	clinical outcome assessment
CO 2	carbon dioxide (bicarbonate)
CONSORT	Consolidated Standards of Reporting Trials
COVID-19	coronavirus disease 2019
CRF	case report form
CrCL	creatinine clearance
CRO	contract research organization
Cr	creatinine
CSF	cerebrospinal fluid
CSR	Clinical Study Report
CT	clinical trial
CTFG	Clinical Trials Facilitation Group
CCI	
DILI	drug-induced liver injury
DKMA	Danish Medicine Agency
eDMC	External Data Monitoring Committee
EC	ethics committee

Abbreviation	Term
ECC	emergency contact card
ECG	electrocardiogram
eCRF	electronic case report form
EDB	exposure during breastfeeding
EDP	exposure during pregnancy
eGFR	epidermal growth factor receptor
EMA	European Medicines Agency
ENT	ear, nose & throat
EQ-5D	EuroQol-5 Dimensions
EQ-5D-Y	EuroQol-5 Dimensions-Youth
EQ-VAS	EuroQol – Visual Analog Scale
EU	European Union
EudraCT	European Clinical Trials Database
FAS	full analysis set
FGFR3	fibroblast growth factor receptor 3
GCP	Good Clinical Practice
GGT	gamma-glutamyl transferase
HIPAA	Health Insurance Portability and Accountability Act
HRQoL	health-related quality of life
IB	Investigator’s Brochure
ICD	informed consent document
ICH	International Council for Harmonisation of Technical Requirements for Pharmaceuticals for Human Use
ID	identification
IDS iSYS	multi-discipline automated system
IGF-1	insulin-like growth factor 1
IMP	investigational medicinal product
IND	Investigational New Drug
INR	international normalized ratio
IP	investigational product
IP manual	investigational product manual
IPAL	Investigational Product Accountability Log
IRB	Institutional Review Board
IRC	internal review committee
IRT	interactive response technology
ISR	injection site reaction
LFT	liver function test
MAD	multiple ascending dose
MCH	mean corpuscular hemoglobin
MCHC	mean corpuscular hemoglobin concentration
MCV	mean corpuscular volume
MRI	Magnetic resonance imaging

Abbreviation	Term
N/A	not applicable
NAb	neutralizing antibodies
NC1	noncollagenous 1
NIMP	noninvestigational medicinal product
CCI	
ObsRO	observer reported outcome
PD	pharmacodynamic(s)
PK	pharmacokinetic(s)
PopPK	population pharmacokinetics
PPAS	per protocol analysis set
PRO	patient reported outcome
PSG	Polysomnography
PT	prothrombin time
CCI	
QD	once daily
CCI	
QTL	quality tolerance limit
QW	once weekly
Rac	geometric mean accumulation ratio
RBC	red blood cell
RNA	ribonucleic acid
SAD	single ascending dose
SAE	serious adverse event
SaO 2	oxygen saturation
SAP	Statistical Analysis Plan
SC	subcutaneous(ly)
SoA	schedule of activities
SOP	standard operating procedure
SRSD	single reference safety document
SUSAR	Suspected Unexpected Serious Adverse Reaction
TA-46	Recifercept alias
TBili	total bilirubin
TMax	time of maximum concentration
TEAE	treatment-emergent adverse event
T 1/2	terminal half-life
ULN	upper limit of normal
US	United States
WBC	white blood cell
WOCBP	woman of childbearing potential

1. INTRODUCTION

This statistical analysis plan (SAP) provides the detailed methodology for summary and statistical analyses of the data collected in Study C4181008. This document may modify the plans outlined in the protocol; however, any major modifications of the primary endpoint definition or its analysis will also be reflected in a protocol amendment.

1.1. Study Objectives, Endpoints, and Estimands

Objectives	Estimands	Endpoints
Primary:	Primary:	Primary:

 Evaluate the long-term safety and tolerability of recifercept doses and dosing regimes in participants aged ≥ 15 m to < 12 years with achondroplasia. 	N/A.	Long-term Safety and tolerability of recifercept as assessed through frequency and severity of AEs/SAEs.

 To assess long-term efficacy of recifercept to increase height growth in children with achondroplasia. 	
 The primary efficacy estimand is intended to provide a population level estimate of the effect of the IP on a continuous endpoint. 
Population-level summary: ratio between participants in the trial and a reference population [Merker et al, 2018]¹ in growth of height at 24 month; ratio between treated and reference population is observed change-from-baseline of treated participants standardized by reference participant given age and gender.
	
 Increase in height growth above expected in reference population [Merker et al, 2018].¹
Secondary:	Secondary:	Secondary:

 To evaluate the PK of recifercept in children aged ≥ 15m to ≤ 12 years old with achondroplasia. 		Population PK characterization in children aged ≥ 15 m to < 12 years old with achondroplasia. CL/F and other PK parameters of recifercept to assess exposures in different age group.

Objectives	Estimands	Endpoints

 To assess efficacy of recifercept to improve achondroplasia-related complications. 		
 Sitting height/standing height ratio. Arm span to height/length difference. Knee height:lower segment ratio. Occipito-frontal circumference. Ratio of occipito-frontal distance to occipito-mid-face measurements. z-score of the above proportionality and skull morphology where achondroplasia reference datasets exist (occipito-frontal circumference, arm span, sitting height). Fixed flexion angles at elbow. Polysomnography parameters in those with pre-existing sleep-disordered breathing at the time of enrollment. BMI. Waist:chest circumference ratio.

 Assess change in individual safety parameters. 		
 Change from baseline in safety labs, vital signs, physical examination. Rate of ADAs.

CCI [REDACTED]
	
[REDACTED]
	
[REDACTED]


[REDACTED]
	
[REDACTED]
	
[REDACTED]

1.1.1. Primary Estimand(s)

The primary estimand is defined according to the primary objective and is in alignment with the primary endpoint. It includes the following 4 attributes:

- Population: Patients with achondroplasia, as defined by inclusion/exclusion criteria;
- Variable: Height Growth at 24 months;
- Height Growth = (Observed Change from Baseline (from study C4181005) in standing height (cm))/(Expected Change from Baseline (cm)[Merker et al, 2018]¹)

- Intercurrent event(s): Withdrawal and all events leading to missing data will be excluded from efficacy analysis and will not have their data imputed;
- Population-level summary: Mean Height growth at 24 months adjusted for age and gender.

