## **7. DISCONTINUATION OF STUDY INTERVENTION AND PARTICIPANT DISCONTINUATION/WITHDRAWAL**

### **7.1. Discontinuation of Study Intervention**

It may be necessary for a participant to permanently discontinue study intervention. Reasons for permanent discontinuation of study intervention include the following:

- Non-compliance with study intervention;
- Pregnancy;
- Withdrawal of consent by parent/guardian;
- Investigator decision to withdraw;
- Death.

Note that discontinuation of study intervention does not represent withdrawal from the study. If study intervention is permanently discontinued, the participant will remain in the study to complete the final follow-up visit. See the [SoA](#) for data to be collected at the time of discontinuation of study intervention and follow-up for any further evaluations that need to be completed.

In the event of discontinuation of study intervention, it must be documented on the appropriate CRF/in the medical records whether the participant is discontinuing further receipt of study intervention or also from study procedures, posttreatment study follow-up, and/or future collection of additional information.

The decision to withdraw the participant from the study ultimately lies with the investigator. For example, occurrence of any clinically relevant sign or symptom that, in the opinion of the Investigator (or designee), warrants participant withdrawal. Additionally, if a participant

experiences a serious or intolerable AE that prevents them from continuing with study participation such as severe injection site reaction or hypersensitivity, this would be expected to lead to withdrawal.

Study intervention will be discontinued if the investigator considers that it is in the participants best interest to initiate any of the prohibited treatments described in [Section 6.8](#).

If study intervention is definitively discontinued, the participant will not remain in the study for further evaluation. See the [SoA](#) for data to be collected at the time of discontinuation of study intervention.

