### *Safety*

The safety data will be summarized in accordance with Pfizer Data Standards. All participants who receive IP (safety population) will be included in the safety analyses. All safety data will be summarized descriptively through appropriate data tabulations, descriptive statistics, categorical summaries, and graphical presentations. Safety endpoints for the study include:

- TEAEs and SAEs;
- Withdrawals from treatment due to AEs.

Change from baseline in laboratory data and vital signs will be additionally summarized. Participant listings will also be produced for these safety endpoints.

The primary efficacy estimand will be the population treatment effect of the mean change-from-baseline of a continuous response (ie, height, growth) at month 24 irrespective of IP compliance. Increase in height growth above expected growth in reference population, a co-primary endpoint, is defined as the height growth in the achondroplasia reference population +50%. Intercurrent event for the efficacy estimand: withdrawal and all events leading missing data will be excluded from efficacy analysis and will not have their data imputed. The population-based treatment effect will be the mean change-from-baseline at Month 24.

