5. ANALYSES AND SUMMARIES

5.1. Primary Endpoint(s)

5.1.1. Increase in height growth above expected in reference population

5.1.1.1. Main Analysis

- Estimand strategy: Hypothetical ([Section 1.1.1](#)).
- Analysis set: FAS ([Section 3](#)).
- Analysis methodology: Change from baseline relative to Merker (2018) will be analyzed using MMRM including data from Months 3-24 with gender (and possibly age), and whether a subject has switched doses of recifercept as covariates, subject (and/or time) as a random effect and an unstructured covariance matrix ([Section 4.2.1](#)).
- Intercurrent events and missing data: Data after study drug discontinuation and rescue will be excluded; intermediate missing values will not be imputed.
- The sample size, mean, standard deviation, median, minimum, and maximum at the baseline and postbaseline visits for observed standing height and change from baseline will be presented for each treatment arm.
- The least-squares (LS) means, the 95% confidence interval for the LS means, the difference between the LS means for each pair of treatment groups, and the corresponding 95% confidence interval will be presented for change from baseline in standing height for all postbaseline visits.

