5.1.1.2. Sensitivity/Supplementary Analyses

The main analysis will be repeated by using the per-protocol analysis set (PPAS) as defined in [Section 5.1.1.1](#). It will use the same methodology and summary as the main analysis.

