8. APPENDICES

Appendix 1. Summary of Efficacy Analyses

Endpoint	Analysis Type	Population	Data Inclusion and Rules for Handling Intercurrent Events and Missing Data	Analysis Model
Change from baseline to Month 24 in mean standing height	Summary	FAS	Separately for observed data and imputed data.	N/A
	Main analysis	FAS	All data collected will be included regardless of intercurrent events. Missing data will not be imputed.	MMRM with terms time,dose, gender & age
	Sensitivity/supplementary analysis	PPAS	All data collected will be included regardless of intercurrent events. Missing data will not be imputed.	MMRM with terms time,dose, gender & age
Change from baseline to Month 12 in mean arm span-height difference	Summary	FAS	Separately for observed data and imputed data.	N/A
	Main analysis	FAS	All data collected will be included regardless of intercurrent events. Missing data will be not be imputed.	MMRM with terms time,dose, gender & age
	Sensitivity/supplementary analysis	PPAS	All data collected will be included regardless of intercurrent events. Missing data will not be imputed.	MMRM with terms time,dose, gender & age

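### The documents give conflicting rules for children who withdraw, and no planned analysis tests the Month 24 growth ratio against departure from missing-at-random

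*SAP*

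**What the plan says.** Four places govern what happens to a child who leaves, and they do not agree.

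- **SAP 1.1.1** (and 1.1.2 for arm span minus height): "Withdrawal and all events leading to missing data will be excluded from efficacy analysis and will not have their data imputed". The protocol synopsis and protocol 9.3.2 carry the same rule.
- **SAP 5.1.1.1**: "Estimand strategy: Hypothetical", with a cross-reference to 1.1.1. The endpoint "will be analyzed using MMRM including data from Months 3-24" on the full analysis set. The data rule is "Data after study drug discontinuation and rescue will be excluded; intermediate missing values will not be imputed".
- **SAP Appendix 1**, main analysis row: "All data collected will be included regardless of intercurrent events". It also lists a summary of imputed data, but gives no imputation method and elsewhere in the table rules imputation out.
- **Protocol 9.3.2**: an ANOVA of the 24-month change in height by dose group, for an estimand defined "at month 24 irrespective of IP compliance".

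The single sensitivity analysis (SAP 5.1.1.2) is the same model on the per-protocol set. In SAP Section 3 that set accepts data complete to discontinuation. In protocol 9.2 it requires complete data to Month 24. SAP 4.3 says other missing-data methods follow, but its only subsection covers PK and a redacted data type.

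**The concern.** The primary efficacy result is an uncontrolled ratio of observed to reference growth. There is no concurrent arm in which selective loss could cancel out, so a shift in who contributes at Month 24 goes straight into the comparison. An analyst could follow SAP 1.1.1 and the protocol and drop every child without a Month 24 height, or follow SAP 5.1.1.1 and keep those children's earlier visits. Each choice can be defended from the text, and they can give different answers.

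Loss related to growth or tolerability is possible under the protocol. Section 7.1 lists "Non-compliance with study intervention" among the reasons for permanent discontinuation, which sits uneasily with an estimand that disregards compliance. The same section stops study drug when a prohibited treatment is to be started, and Section 6.8.1 counts growth hormone among those. Section 6.5 provides for discontinuation when tolerability problems continue at the lowest dose. Whatever the pattern turns out to be, nothing planned would show how far the ratio depends on it.

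**Working it through.** The plan states no dropout rate, no SD for the growth ratio and no power calculation, so it has no figure to reproduce. From the documents: about 63 children, three doses, three-monthly heights to Month 24, and a benchmark of reference growth plus 50% (ratio 1.5). Every other input below is assumed.

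**1. Bias of a completers mean.** Let d be the fraction withdrawing, and C and W the mean full-period ratios of completers and leavers. The all-children mean is (1 − d)C + dW, so the completers mean exceeds it by d(C − W).

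| Withdrawal d | C − W = 0.1 | 0.3 | 0.5 |
|---|---|---|---|
| 10% | 0.01 | 0.03 | 0.05 |
| 20% | 0.02 | 0.06 | 0.10 |
| 30% | 0.03 | 0.09 | 0.15 |

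Against the protocol's benchmark: if completers average exactly 1.50 and leavers 1.0, the all-children mean is 0.9 × 1.5 + 0.1 × 1.0 = 1.45 at 10% withdrawal, 1.40 at 20% and 1.35 at 30%.

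**2. Completers mean against an MMRM-type estimate.** A simulation used 63 children pooled over doses, eight visits, mean ratio 1.3, between-child SD 0.3, measurement error 0.06 of a year's expected growth, and slower growers more likely to leave (1,500 runs per cell). The MMRM-type estimate is the maximum-likelihood Month 24 mean with unstructured covariance. Entries are bias in the ratio against the all-children mean.

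| Dropout driven by | Dropout | Completers | MMRM-type |
|---|---|---|---|
| last observed ratio (missing at random) | 11 / 22 / 32% | +0.034 / +0.067 / +0.098 | 0.000 at each |
| latent growth | 11 / 21 / 31% | +0.031 / +0.063 / +0.093 | +0.002 / +0.005 / +0.009 |
| last observed ratio, reference-rate growth afterwards | 11 / 22 / 32% | +0.035 / +0.073 / +0.109 | +0.001 / +0.005 / +0.011 |

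The choice of rule therefore moves the ratio by roughly 0.03 to 0.10, while the MMRM's own residual is about 0.01 or less.

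**3. Leavers who responded like the others.** Suppose leavers had the same on-drug ratio of 1.25, left at fraction t of the period and then grew at the reference rate. The all-children mean is (1 − w) × 1.25 + w × (1 + 0.25t), where w is the fraction leaving. The gap from 1.25 is 0.25 × w × (1 − t). At w = 20% and t = 0.5 it is 0.25 × 0.2 × 0.5 = 0.025. Over w = 10–30% and t = 0.25–0.75 it runs from 0.25 × 0.1 × 0.25 = 0.006 to 0.25 × 0.3 × 0.75 = 0.056. This is the distance between two estimands (growth had the child stayed on drug, and growth whatever happened). It is not a bias of the MMRM for the hypothetical estimand that SAP 5.1.1.1 names.

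**4. What the per-protocol rerun can show.** It applies the same likelihood and the same missing-at-random assumption to a subset. Under either definition of the set, it does not vary what is assumed about heights after withdrawal.

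**The case against.** The best defence is that SAP 5.1.1.1 labels the strategy hypothetical and points back to 1.1.1. On that view the exclusion means later data only, and an MMRM on data up to discontinuation fits it. That model already adjusts for loss explained by observed growth, and its residual bias above is small. The study is an open-label extension with no statistical hypotheses (SAP 4.1). Entrants have completed the parent study and are judged to have a positive risk–benefit profile, so some intolerant children have probably already gone. Lack of efficacy is marked not applicable as a discontinuation reason (protocol 7.1.4).

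Much of this stands. The estimand sentence is ambiguous, and the MMRM as described is a sound primary model. But the defence does not reach the protocol, where the same exclusion sits beside an ANOVA that only children with a Month 24 height can enter. Nor does it reach Appendix 1, which contradicts the hypothetical strategy. The small residual also depends on inputs that no planned analysis examines.

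Two stronger readings are tempting. A reader might infer that the per-protocol rerun removes still more non-compliers and so can only favour the drug. The SAP's set can retain discontinuers and never mentions compliance, and the deviation list in Appendix 2.3 has no content. Excluding a child who received a prohibited growth treatment could lower the ratio, so the direction is unknown. A reader might also infer that poor growers will be the ones to leave. No document says so; it is an assumption.

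**Conclusion.** The point holds as a conflict of rules and a missing sensitivity analysis. It does not show that the planned MMRM is materially biased. If the exclusion is followed literally, the completers mean is open to an overstatement of 0.01–0.05 at 10% withdrawal, 0.02–0.10 at 20% and 0.03–0.15 at 30%, provided leavers' full-period ratio is 0.1–0.5 below that of completers. If SAP 5.1.1.1 is followed, the residual was about 0.01 or less in the scenarios simulated. The gap of about 0.025 (0.006–0.056) in step 3 should not be reported as an error of the MMRM; it shows why the estimand must be fixed first.

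All these sizes rest on assumed dropout, response and variability. The MMRM result also presumes a Month 24 mean from the model in SAP 4.2.1. The sample code in SAP Appendix 4 has no dose-by-month term and requests dose means averaged over visits, so it would not return that quantity. With no hypothesis test at stake this is not fatal, but it should be settled before analysis.

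**What to change.** 1. In SAP 1.1.1 and 1.1.2, replace the exclusion with a rule such as: all observed heights up to withdrawal are used; later heights are missing and are handled by the MMRM. State one intercurrent-event strategy. Align SAP 5.1.1.1, 5.2.1.1 and Appendix 1, the two per-protocol definitions, and the protocol synopsis and 9.3.2 (including the ANOVA) with it.
2. Prespecify one missing-not-at-random sensitivity analysis of the Month 24 ratio. One option is multiple imputation in which growth after withdrawal follows the age- and sex-specific reference increment (ratio 1.0), reported with its confidence interval beside the MMRM. A delta or tipping-point analysis would also serve. Keep the per-protocol rerun as supplementary.
3. Reconcile the two statements in protocol 7.1 on children who stop study drug: one keeps them in the study to the final follow-up visit, the other says they do not remain for further evaluation. This determines whether later heights exist.

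The cost is one extra analysis, using reference values the endpoint already needs (SAP Appendix 2.2), and aligned protocol wording at the next amendment. The reported ratio may be slightly less favourable.
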